In phase 2, we will complete a pilot randomized controlled trial comparing MAP to CBT that will allow us to estimate initial treatment effects and determine if a future, large-scale trial is warranted.

Section 6 - Specific Aims

6) Provide a statement of specific aims and hypotheses that serve as the basis for this protocol. Emphasize those aspects that justify the use of human subjects.

This proposal seeks to develop and initially evaluate an integrated, model-driven mindfulness-based intervention for chronic pain, Mindful Action for Pain (MAP), designed to help Veterans with chronic pain achieve sustained functional changes driven by personal values. To accomplish this, we have chosen the psychological flexibility (PF) model. PF refers to the ability to behave consistently with one's values even in the face of unwanted thoughts, feelings, and bodily sensations such as pain. The PF model is especially applicable to chronic pain because of its ultimate goal of supporting increased engagement in meaningful life activities. MAP is unique in that it integrates evidence-based treatment methods from Mindfulness-Based Stress Reduction (e.g., formal mindfulness meditation), Acceptance and Commitment Therapy (metaphors and experiential exercises), and Dialectical Behavior Therapy (e.g., informal mindfulness techniques) within a group-based delivery approach that is guided by the PF model. This application seeks to develop MAP (Phase 1) and conduct a pilot randomized trial of MAP vs. CBT for chronic pain (CBT-CP) (Phase 2).

Aim 1: Fully develop MAP in a population of Veterans with chronic pain (Phase 1).

Aim 2: Evaluate the feasibility of a future randomized efficacy trial of MAP vs. CBT-CP (Phase 2).

Hypothesis 1: MAP and CBT-CP will be feasible to deliver, as evidenced by attainment of recruitment goals, retention rates > 80%, and high credibility and expectancy ratings.

Aim 3: Estimate the preliminary impact of MAP and CBT-CP to determine if a future efficacy trial is warranted.

Aim 4: Explore the relationship between meditation adherence and treatment outcomes.

Aim 5: Explore objective measures of physical activity (actigraphy) at baseline and post-intervention as a potential future index of functional outcomes.

Section 7 - Background and Significance

7) Provide a succinct discussion of relevant background information to justify performing the proposed study.

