Sample size for Phase 2: In Phase 2, we will conduct 12 groups (6 MAP and 6 CBT-CP) with 7 - 8 Veterans in each group to examine the feasibility of a future RCT and preliminary response to MAP (year 3 = 4 groups; year 4 = 6 groups; year 5 = 2 groups). Anticipating up to a 20% attrition rate, 86 participants will be recruited for Phase 2.

Number of Visits: Visit 1: Consent, MINI, baseline measures and actigraphy; Visits 2 - 9: MAP or CBT-CP sessions 1 - 8; Visit 10: Posttreatment measures, actigraphy; Visit 11: 3-month follow-up measures (may be done by phone); Visit 12: 6-month follow-up interview using Microsoft Teams.

Interventions. An overview of the MAP intervention is described below, as well as the CBT-CP intervention. Both groups use an 8-week, 90-minute session protocol. The MAP intervention will be delivered solely by the PI. The PI is a licensed clinical psychologist with several years of experience conducting group and individual therapy for chronic pain using mindfulness-based techniques. For the CBT-CP intervention (Phase 2 only), we will use a manualized protocol developed at the VASDHS used in previous research (Wetherell et al., 2011). In the second half of Year 2 of the award, a part-time study therapist will be hired and trained to deliver the CBT-CP intervention. This therapist will be required to have graduate (at least master's level) training in psychology, and will be recruited within the expansive VASDHS and UCSD communities. The study therapist will be supervised by [name] (co-investigator), who is a certified CBT-CP VA provider and the current supervisor for trainees in the Behavioral Medicine clinic that provide group-based CBT-CP at the VASDHS. [name] will train the study therapist and ensure competency prior to the start of Phase 2. The study therapist will have weekly check-ins with [name] via in-person or telephone while facilitating CBT-CP groups to ensure minimal drift from the protocol and to answer any questions that arise.

Description of MAP

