In MAP, participants are first exposed to mindfulness (paying attention in a particular way: on purpose, in the present moment, without judgement) and instructed how to engage in formal practice (session 1). Similar to other formal mindfulness meditation interventions, MAP consists primarily of two principal techniques: sitting meditation and body scan meditation. Briefly, sitting meditation consists of focusing attention on the sensations of breathing, noticing when the mind has wandered from the breath, briefly noting the source of wandering (e.g., "pain in shoulder," "thinking," etc.), and returning attention back to the sensation of breathing. The body scan meditation entails sustaining and moving attention around specific body parts starting at the toes and ending at the head (or vice versa). Similar to sitting meditation, when the practitioner notices the mind has wandered, the source of wandering may be briefly noted and attention is returned to the body. Starting after the 1st session, Veterans are expected to engage in daily formal mindfulness meditation, at first using provided audio recordings and later without recordings, and complete a daily meditation diary. Home meditation practice will follow a similar protocol as other meditation-based interventions at the VA. Specifically, Veterans will have access to audiotapes that vary in duration (5 - 20 minutes) via the Lifedata application or audio CD if preferred for the sitting and body scan meditations. Audio instructions are provided by [name] and links to publicly available guided meditations. This will enable the most control over meditation instruction and allow alterations to instructions during Phase 1. Sample meditation scripts are provided in 27. *Attachments*.

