Initially, chi-squares and Analysis of Variance will be used to assess the effectiveness of the randomization procedures by comparing participants in each treatment condition on baseline variables. Within-group change will be assessed separately in MAP and CBT-CP groups on the primary (pain interference) and secondary clinical outcomes (pain acceptance, trait mindfulness, pain catastrophizing). We will plot means and standard deviations overtime to examine them visually, and determine the percentage of participants in each group that achieve minimally clinically important change on the BPI Pain Interference scale (1-point change, etc.). Additionally, we will use linear mixed-effects (LME) models to explore preliminary estimates of treatment effects. Time will be added as fixed effects in models, and the intercept will be added as a random effect. Effect size for within-group change will be calculated according to procedures described by Cohen, and interpreted with caution and in the context of the 95% confidence interval that surrounds it. The preliminary within-group treatment effects of MAP will help determine our future directions. For example, medium-large treatment effects would provide signal for future testing

whereas small treatment effects would suggest a need for additional development. Within the CBT-CP group, treatment effects will be examined in relation to findings from other published pain trials with similar Veteran populations to ensure adequacy of CBT-CP delivery.

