We will also conduct preliminary between-group comparisons on the BPI Pain Interference measure to better understand if continuing to pursue evaluation of MAP is warranted. Given that functional improvement is the ultimate goal of this research, we chose pain interference as the key outcome for the preliminary between-group analyses and power calculations because it is a proxy for functional improvement and one of the most commonly used outcome measure in psychosocial intervention trials of chronic pain. Group comparisons will be examined via LME with group (MAP vs. CBT-CP), time (10-total time points: baseline [1 time point], weekly during sessions [8 time points], post-intervention [1 time point]), and the treatment by time interaction added as fixed effects. The intercept will be added as a random effect. Effect size for the difference between groups will be calculated according to procedures described by Cohen. Effect size will be interpreted with caution, and in the context of the 95% confidence intervals that surrounds it.

Average time spent per week in meditation practice will be calculated from the LifeData mobile application or daily weekly diaries. The relationship between meditation practice time and study measures will be explored by adding the adherence rate to LME models as a covariate.

The actigraphy outcome will be the total activity count from each active interval, averaged across each 7-day observation period, excluding periods of missing data that occur due to temporary removal of the device. We will exclude participants that wear the Actiwatch < 5 valid days, with valid days defined as periods with < 4 hours of missing data. Participants will be instructed to press the event marker button on the Actiwatch to denote the times they get into and out of bed. Rest intervals (analogous to time in bed) will be scored manually using event markers, activity, and light, following the methodology of Patel et al. (2015), which takes into account that participants sometimes forget to press the event marker. Actigraphy data will be explored visually and via LME for trends of increased activity levels from baseline to post-intervention within group (Phase 1 and 2) and between groups (Phase 2) with guidance from [name] (statistical consultant), who has previous experience analyzing actigraphy data.

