9.8) Provide the name and a reference for questionnaires/surveys that are standard or identify them here and attach a copy of the questionnaire/survey. *Questionnaires or surveys that are not clinical standard references must be uploaded. Reference the help link for additional information related to surveys administered to VA personnel and approved platforms for web-based surveys.*

See also attachment for tables of assessments by visit.

Eligibility:

- The PEG (Krebs et al., 2009) is a brief pain screening instrument developed from the Brief Pain Inventory (described below). The PEG contains one item that assesses pain intensity (P), and two items that assesses pain interference: interference with enjoyment of life (E), and interference with general activity (G). In order to be eligible for the study (both phases),

participants must score >4/10 on both pain intensity and one or both of the pain interference items.

- Mini International Neuropsychiatric Interview (MINI; Lecrubier et al., 1997): 15 - 30 minute interview used to identify the exclusionary conditions of current psychosis, mania, substance abuse within the past year, and suicidality. It also will be used to determine current and lifetime major depression, generalized anxiety disorder, and PTSD for descriptive purposes. The MINI will be administered only at the baseline assessment by the PI.

Phase 1 Only:

-Reactions to class material and practices (logic, understandability, applicability, and self-efficacy)

All Phases:

- Demographics: age, gender, race/ethnicity, relationship status, years of education, SES/income /living situation, occupation/work status, branch of service/highest rank

- Credibility/Expectancy Questionnaire (CEQ; Borkovec & Nau, 1972), given at end of 1st session to assesses how logical the treatment seems to the participant and how much they expect to benefit from it

- Client Satisfaction Questionnaire (CSQ-8; Larsen et al., 1997) 8-items

- Practice diary to determine average time spent per week in meditation practice (MAP group only). Participants will have option of using LifeData app to record daily meditation).

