- Brief Pain Inventory (BPI; Cleeland & Ryan, 1994). The BPI consists of two subscales: pain severity (4-items) and pain interference (7-items). This questionnaire will be administered at the baseline assessment, weekly during the intervention (using the Polls function on WebEx), and at the post-intervention assessment. The Polls function on WebEx allows for participants to complete the BPI at the beginning of the session. Participants cannot see the responses of others. The Polls are saved on the PI's R drive located behind the VA firewall.

- Chronic Pain Acceptance Questionnaire (CPAQ; McCracken, Vowles, & Eccleston, 2004). 20-items

- Pain Catastrophizing Scale (PCS; Sullivan Bishop, & Pivik, 1995). 13-items

- Medical Outcomes Study 12-Item Short Form Health Survey (SF-12; Ware, Kosinski, & Meller, 1996). 12-items

- Patient Health Questionnaire (PHQ-9; Spitzer, Kroenke, & Williams, 1999). 9-items

- PTSD Checklist for DSM-5 (PCL-5; Bovin et al., 2016). 20-items

- Mindful Attention and Awareness Scale (MAAS; Brown & Ryan, 2003). 15-items

- Adverse Childhood Experience Questionnaire (ACE; Centers for Disease Control and Prevention, 2008). 10-items

- Injustice Experience Questionnaire (IEQ; Sullivan et al., 2008). 12-items

- Cognitive Fusion Questionnaire (CFQ; Gillanders et al., 2014). 7-items

- Insomnia Severity Index (ISI; Morin, 1993). 7-items

- Chronic Pain Values Questionnaire (CPVQ; McCracken & Yang, 2006). 12-items

- Medication will be recorded at the baseline (Visit 2) and post-intervention assessments (Visit 11). Participants will be asked to have all medication bottles, including over-the-counter medications and dietary supplements, available at their assessment appointments.

- Medication/treatment changes and adverse events will be assessed weekly. Participants will be asked if they made any medication/treatment changes over the last week and if any adverse events occurred.

- Actigraphy. The Actiwatch Spectrum PRO (Phillips Respironics, Bend, Oregon) will be used as an objective measure of physical activity. The Actiwatch Spectrum PRO will be worn continuously on the non-dominant wrist for two one-week periods at baseline and post-intervention in both phases by all participants.

-6-month interview questions:

Example questions:

1. What has been the most helpful part of the group for your pain?
2. When engaging in day-to-day activities, how are you able to manage pain?

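### Aim 4 enters practice time only as a covariate; with one average per person, its coefficient mixes starting pain interference with change

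*Combined protocol and SAP*

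**What the plan says.** Section 6 states the aim: "Aim 4: Explore the relationship between meditation adherence and treatment outcomes". The whole analysis for it is two sentences in Section 9, Data and Data Analysis (Phase 2). The first defines the measure: "Average time spent per week in meditation practice will be calculated from the LifeData mobile application or daily weekly diaries". The second gives the method: "The relationship between meditation practice time and study measures will be explored by adding the adherence rate to LME models as a covariate".

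The models to which it is added are described just before. For the within-group model: "Time will be added as fixed effects in models, and the intercept will be added as a random effect". The between-group BPI model adds group and treatment-by-time. It uses ten time points (baseline, eight weekly sessions, post-intervention), so baseline is an outcome row and not an adjustment variable. The only interaction named is treatment-by-time.

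Two timing statements matter. Section 9, Description of MAP: "Starting after the 1st session, Veterans are expected to engage in daily formal mindfulness meditation". Section 9.8, on the BPI: "The Polls function on WebEx allows for participants to complete the BPI at the beginning of the session".

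Section 9.8 lists the meditation diary for the MAP group only. Section 27a says that both arms log daily practice in the app.

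**The concern.** Aim 4 is about treatment outcomes, and an adherence result from this trial would naturally be read as dose-response: those who practised more improved more. A person-constant covariate without a time interaction shifts all of a person's scores by the same amount, so it cannot represent different change at different levels of practice. For treatment group the plan includes the interaction with time; for practice it does not.

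Two of the ten BPI rows also precede any home practice. These are baseline and session 1, since practice starts after session 1 and the BPI is completed as each session begins. If people who start with more or less pain interference practise differently, the coefficient can show an association when practice has nothing to do with change, or hide one that exists.

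**Working it through.** The documents give no SD, correlation or expected coefficient for Aim 4, so there is no stated figure to reproduce. The algebra follows from the model; the sizes rest on assumed inputs.

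**1. What the coefficient estimates.** Let A be one practice value per person. Let b0 be its association with baseline, bc its association with total change, and f(t) the share of change reached at row t. In a random-intercept model with complete data, the coefficient of a person-constant covariate is the regression of each person's mean score on A:

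coefficient = b0 + bc × mean f(t)

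**2. Weight given to change over the ten rows (t = 0 to 9).**

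- Linear from baseline: (0 + 1 + … + 9)/(9 × 10) = 45/90 = 0.50
- Linear from session 1: (0 + 0 + 1/8 + … + 8/8)/10 = 4.5/10 = 0.45
- Complete by t = 3: 8/10 = 0.80; by t = 4: 7.5/10 = 0.75
- Starting after t = 3: 3.5/10 = 0.35; after t = 5: 2.5/10 = 0.25

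The baseline association always enters at full weight.

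**3. Apparent association when practice is unrelated to change.** Assumed: intercept SD 1.5, residual SD 1.2, slope SD 0.1 per row, practice standardised. With 86 recruited and 1:1 allocation, n = 43 in MAP, or about 34 after 20% attrition.

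- Variance of the person mean = 1.5² + (4.5 × 0.1)² + 1.2²/10 = 2.25 + 0.2025 + 0.144 = 2.60; SD 1.61.
- A practice-baseline correlation of 0.2 becomes 0.2 × 1.5/1.61 = 0.19 with the person mean; 0.3 becomes 0.28.
- By Fisher's z at n = 43, these give about 22% and 44% significant at the two-sided 5% level.

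Simulation (8,000 MAP arms per setting) agrees:

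| Practice-baseline correlation | n = 43 | n = 34 |
|---|---|---|
| 0 | 5% | 5% |
| 0.1 | 9% | 8% |
| 0.2 | 23% | 19% |
| 0.3 | 45% | 37% |

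Varying intercept SD from 1.0 to 2.0 and residual SD from 0.8 to 1.6 gives, at n = 43, 18–23% at correlation 0.2 and 37–47% at 0.3. REML fits with 20% dropout gave 5.0%, 21.9% and 44.1% at correlations 0, 0.2 and 0.3.

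**4. A true association with change (bc = -0.6 by post-intervention, linear).**

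- Correlation 0: 0 + 0.50 × (-0.6) = -0.30
- Correlation +0.2: 0.2 × 1.5 - 0.30 = 0.00
- Correlation -0.2: -0.30 - 0.30 = -0.60, which matches the truth only by coincidence

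Over the other trajectories the range is -0.15 to -0.48 at correlation 0, and +0.15 to -0.18 at +0.2.

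**5. Check with different assumptions.** Mixed-model fits (200 runs per case, n = 43, baseline SD 1.8, change SD 0.8, residual SD 1, linear from session 1) gave:

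| Case | Covariate, expected | Covariate, mean | p < 0.05 | Practice-by-time, mean |
|---|---|---|---|---|
| b0 = -0.6, bc = 0 | -0.60 | -0.61 | about 60% | -0.01 |
| b0 = 0, bc = -0.6 | -0.27 | -0.28 | 19% | -0.61 |
| b0 = +0.3, bc = -0.6 | +0.03 | +0.02 | 4.5% | -0.61 |

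The interaction separates change from starting level in all three cases.

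**6. The random slope is needed for the ten-row BPI.** With the planned random intercept only, the practice-by-time test rejects in about 10% of null trials under the assumptions in step 3 (6% at slope SD 0.05, 17% at 0.15), and in 17% under those in step 5. With a random slope, n = 43 and 20% dropout, it rejects in about 5% (Wald z) or 4% (Satterthwaite), with power of 65–68% for -0.6. At n = 34 the figures are 4–5% and 59–62%. A linear practice-by-time term recovers 84–108% of the total change association under the trajectories in step 2.

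**7. Measures with two or three scores.** The covariate gives 15–19% false positives at correlation 0.2 and 31–39% at 0.3. Practice-by-post with a random intercept gives 5% (two scores) or 6% (three).

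**The case against.** The strongest objection is that the text does not fix the reading. Practice is logged daily, so weekly values will exist, and a week-by-week covariate mixes level and change much less: simulated false positives are 5–7% at correlation 0, 6–10% at 0.2 and 7–11% at 0.3. This stands as a condition on the concern. However, a weekly average that is then called an adherence rate points to one value per person, and the ambiguity itself needs resolving.

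Second, Aim 4 is exploratory, with no hypothesis, alpha or decision attached, and the analysis sentence speaks of study measures rather than change in them. This limits the consequence. It does not make the coefficient interpretable as an association with improvement, which is how Section 9 otherwise uses these measures when judging whether MAP deserves a larger trial.

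Third, the sizes depend on correlations that nothing in the documents supports. At correlation 0 the test keeps its 5% level, although the estimate is still diluted. At a negative correlation the mixing inflates the coefficient instead of cancelling it. Both points are right; the mixing itself does not depend on the assumed values.

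**Conclusion.** The concern holds on the reading of one average per person. Followed as written, the method yields a coefficient that contains the full baseline association and 0.25 to 0.80 of the association with change (0.50 if change is linear and the rows equally spaced and complete). It therefore does not answer Aim 4.

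How far this misleads depends on the unknown correlation between practice and starting pain interference: it causes only dilution at 0, but about one trial in five shows a spurious association at 0.2 and nearly half at 0.3 with n = 43. These are illustrations under assumed SDs. The damage is confined to interpretation of the adherence result; the comparison of MAP with CBT-CP is not affected. The change is worth making before analysis.

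**What to change.** - State whether adherence is one value per person or one per week, and define the adherence rate in relation to average practice time.
- Name the group analysed. The meditation diary is MAP only, so the within-MAP model is the natural one; reconcile this with Section 27a, where both arms log practice.
- Fit practice, time and practice-by-time. Report practice-by-time with its 95% CI as an exploratory, observational association.
- For the ten-row BPI, add a random slope for time and use small-sample degrees of freedom such as Satterthwaite. If the model does not converge, regress each participant's fitted slope on practice.
- For other measures, match the random effects to the number of visits; a random intercept is enough with two scores.

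Modelling the post-intervention score on practice with adjustment for baseline would be a simpler route to the same question; its power was not evaluated here.

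The cost is SAP wording and one or two model terms, with no new data. The main risk is convergence at n of about 34 to 43: test fits with time coded 0–9 and default settings converged in 72–78% of trials, against at least 99.9% with time scaled 0–1, so the scaling should be specified. The person-slope fallback loses power under 20% dropout (45–47%, against 65% for the random-slope model).

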Phase 2: Data from subject tracking logs will be used to determine the proportions of Veterans 1) who agree to be contacted out of the number approached about the study (general interest in the study), 2) who consent out of the number contacted (willingness to participate in the trial), 3) who attend the initial group meeting out of the number consented (enrollment), 4) who attend each class and complete the intervention out of the number who began (retention), and 5) reasons given for discontinuation. The number of contacts based on various recruitment strategies also will be recorded. Additional feasibility data includes: rate of missing data between treatment groups and per time point; differences in retention rate between treatment groups; factors influencing retention rate and their impact on study outcomes; completion of study measures and homework; and participants' satisfaction with study procedure and treatment delivery method. Further, age, gender, race/ethnicity, medications (including pain and other medications), and changes to medications/chronic pain treatments (TENS, injections, etc.), as well as pain etiologies (collected via chart review) will be explored within and between groups as they relate to study measures. This information will be helpful for assessing the feasibility of MAP and future hypothesis generation.

Additionally, we will examine the preliminary impact of MAP on pain interference (primary outcome), as well as pain acceptance, trait mindfulness, and pain catastrophizing (secondary outcomes). Other questionnaires that will be measured are listed in the *Questionnaires* section. Changes on these measures as well as participant satisfaction would also serve as indicators that MAP may be worthy of a future large-scale RCT.

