- 1) To minimize the risk of patient discomfort, confidentiality will be stressed, participants will be offered breaks as needed, they will be informed that they have the right to refuse to answer questions or to terminate their participation in the study at any time without prejudice, and everyone who interacts with participants will be trained and supervised. Clinical staff will be available if immediate in-person evaluation is required for medical or mental health issues.
- 2) To minimize the risk of patients becoming more anxious or depressed, every patient will be given a 24-hour contact phone number to call in the event of increased depression or anxiety. If these symptoms are detected by either the research coordinator, research assistant, or the person conducting the intervention, [name], licensed psychologist and co-investigator, will be available to evaluate the patient and refer to appropriate treatment and notify the patient's other health care providers. When in doubt, the decision whether continued participation in the study is safe and clinically warranted will always be on the side of patient safety. Adverse events, including those unlikely to be the result of participation in the research (e.g., hospitalization due to an automobile accident), will be monitored at every study contact, including therapy as well as assessment sessions. They will be reported to the appropriate human subjects committees as per policy and to the Data Safety Monitoring Board for this study within the required time frame.

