- 3) Veterans that report suicidal ideation at assessment or baseline/post-treatment assessment via the PHQ-9 or verbally will be further evaluated by the PI and [name]. Subsequent action will depend on the level of threat presented by the Veteran and may range from making a safety plan to implementing 5150 procedures for an inpatient hold. Further, suicidal ideation will be closely monitored during treatment by clinical observation and through comprehensive suicide risk assessments, which are part of standard VA care. Participants who develop suicidality during the treatment will be evaluated by the PI and [name] to determine whether continued participation in the study is safe and clinically warranted. If we and the participant believe that continued participation is contraindicated, an endpoint evaluation will be done and the participant will be referred for appropriate treatment. Appropriate treatment will depend on level of threat, and may include recommending a different form of psychotherapy that more directly addresses the predominant concern (e.g., depression, anxiety, PTSD, sleep, etc.), a referral to the participant's primary care provider or psychiatrist for medication management, referral to the Suicide Prevention Program at the VASDHS for passive suicidality, and/or hospitalization for imminent threat of suicide.
- 4) For participants who wish to terminate prematurely, we will request a final meeting to assess clinical status and safety and to review reasons for withdrawal (if the participant is willing to share them). Referrals for alternative mental health services, including those outside this protocol, will also be provided. Participants enrolled in the study may withdraw at any time without penalty or loss of any benefits or treatment options available to them. Investigators may also withdraw a participant from the study for treatment non-compliance or a newly developed psychiatric or medical problem if, in the opinion of myself and the study team, these factors interfere with the participant's ability to participate fully in the study. If a participant discontinues the study for any reason, he/she will be offered and allowed access to any care in our clinics that any other patient not associated with the study would receive.

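### The weekly question on treatment changes looks back only one week, so changes in a missed week or after attendance stops are not reliably captured

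*Combined protocol and SAP*

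**What the plan says.** Section 9.8 (Questionnaires & Surveys) sets the frequency: "Medication/treatment changes and adverse events will be assessed weekly". The next sentence gives the content: "Participants will be asked if they made any medication/treatment changes over the last week and if any adverse events occurred". The one-week window is attached to medication and treatment changes. The adverse-event clause carries no window.

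The Phase 2 visit list in Section 9 has consent and baseline at Visit 1, sessions at Visits 2 to 9, post-treatment at Visit 10, and then "Visit 11: 3-month follow-up measures (may be done by phone); Visit 12: 6-month follow-up interview using Microsoft Teams". No other contact is listed during treatment.

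Other places bear on capture:

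- Section 9.8: "Medication will be recorded at the baseline (Visit 2) and post-intervention assessments (Visit 11"), with medication bottles at hand.
- Section 15, item 2, on adverse events: they "will be monitored at every study contact, including therapy as well as assessment sessions".
- Section 15, item 4, for those who wish to leave early: "we will request a final meeting to assess clinical status and safety and to review reasons for withdrawal".
- Section 9, Data and Data Analysis, Phase 2: the items to be explored within and between groups include "changes to medications/chronic pain treatments (TENS, injections, etc.), as well as pain etiologies (collected via chart review").

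That last section also plans to look at missing data by group and time point, and at retention by group. Section 9.8 refers to an attached table of assessments by visit, which is not in the reviewed text.

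**The concern.** A fixed look-back works only if the question is put every week. A Veteran who misses one session and attends the next is asked about the most recent week, so the skipped week is not asked about. A Veteran who stops coming without saying so has no listed contact until the post-treatment assessment.

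The lost weeks may not be typical ones. A flare or a new pain treatment is a plausible reason for absence. The protocol treats co-treatment as important: Section 10 excludes Veterans whose pain or mood treatment changed in the month before baseline, and Section 9 sets out to explore changes between groups. Each arm has its own therapist (Section 9, Interventions and Treatment Fidelity), so a difference in attendance is possible. In that case a difference in recorded treatment changes would partly reflect how often Veterans were asked.

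**Working it through.** **1. Figures in the plan.** The documents give no attendance rate, rate of treatment change or capture rate, so there is no figure to reproduce. The usable inputs are 86 participants recruited for Phase 2, 8 weekly sessions, and attrition of up to 20% (all Section 9). Every other rate below is an assumption.

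**2. What each other route recovers.**

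- *Post-intervention medication record.* It shows drugs in use at that time. It need not show a drug started and stopped in between, and a bottle check does not show TENS or an injection. The Veteran must also attend. The visit labels conflict as well: Section 9.8 puts these records at Visits 2 and 11, whereas the Phase 2 list makes Visit 2 a session and Visit 11 the 3-month follow-up. The two must be reconciled.
- *Final meeting.* It is requested from those who wish to terminate and depends on their agreement. A silent non-attender is not clearly included.
- *Chart review.* The parenthesis in Section 9 may cover treatment changes or only pain etiologies. This is the one route that does not need the Veteran to attend or agree to a contact.
- *Adverse events at every contact.* With no stated window, a later contact can pick up an earlier event, but only once a contact takes place.

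**3. Weeks at risk.** Phase 2 has 86 × 8 = 688 person-weeks. At an assumed 90% attendance, 0.10 × 688 = 69 are not asked about in that week; at 80%, 0.20 × 688 = 138. As a cross-check, if the anticipated 20% left halfway on average (assumed), 0.20 × 86 × 4 = 69 person-weeks would be lost before any sporadic absence.

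**4. Effect on a comparison of arms.** Let *a* be the share of weekly inquiries completed and *b* the share of missed-week changes recovered later by another route. The recorded share is *a* + (1 − *a*)*b*. With equal true rates, and changes unrelated to absence, the ratio of recorded changes at 90% against 70% attendance is:

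| Recovery *b* | Arm at 90% | Arm at 70% | Ratio |
|---|---|---|---|
| 0 | 0.90 | 0.70 | 0.78 |
| 0.5 | 0.90 + 0.10 × 0.5 = 0.95 | 0.70 + 0.30 × 0.5 = 0.85 | 0.89 |
| 0.8 | 0.90 + 0.10 × 0.8 = 0.98 | 0.70 + 0.30 × 0.8 = 0.94 | 0.96 |

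With equal attendance, and the same *b* in both arms, the ratio is 1.00 for any *b*. Over assumed pairs of 80–90% against 60–80%, where the arms differ, it runs from 0.67 to 0.89 at *b* = 0 and from 0.94 to 0.98 at *b* = 0.8. If changes cause absence, the recorded share falls further than these figures show.

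**The case against.** The strongest reply is that the text never ties this inquiry to the session. It says only that it is weekly, while the same section states outright that the BPI is completed at the start of the session. Telephone collection appears in the temporary COVID procedures in Section 9 and in Section 27a, so staff may already ring absentees, and the attached visit table may say so. This stands in part: session-only collection is an inference. But the sessions are the only visits listed in that period, and no visible text covers a missed week. The one-week window is stated outright.

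A reader might go further and infer that whatever happens in a missed week is never picked up, and that the arm with poorer attendance will look safer. The documents do not support that:

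- The one-week window is not worded for adverse events, which are also monitored at assessments.
- A final safety meeting is requested from those who wish to leave.
- Medication is recorded again after the intervention, and chart review may add to it.
- No between-arm comparison of adverse events is described, so there is no planned safety contrast to bias.

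Nor can the 0.78 ratio be read as an expected bias, since it needs both an unequal attendance split and zero recovery. It is also fair that the exploration serves feasibility and hypothesis generation, and that missing data and retention by group are to be examined.

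**Conclusion.** The point holds for medication and treatment changes. Followed as written, the one-week look-back leaves changes in a missed week unasked about. The other routes recover some, but not dependably those that are short-lived or non-drug. For adverse events the remaining concern is mainly late capture in Veterans who stop attending without notice.

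Distortion between arms is conditional on attendance differing and recovery being incomplete. Under the assumed 90% against 70% split it ranges from a ratio of 0.78 with no recovery to 0.96 with 80% recovery, and it vanishes if attendance and recovery are equal. The documents supply neither attendance nor recovery. In a pilot where these data are exploratory, this is a low-severity improvement, worth making because it costs so little.

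**What to change.** - In Section 9.8, word both questions as *since we last asked you*, and put them at the post-intervention assessment too. The rewording is essentially free and covers sporadic absence.
- Where feasible, have existing staff ask the same two questions by telephone when a session is missed or attendance stops, through the last scheduled session. At an assumed 80–90% attendance this is roughly 70 to 140 short calls over Phase 2 (from the 69 and 138 person-weeks above). That staff time is the main cost.
- State in Section 9 whether chart review covers treatment changes or only pain etiologies, and reconcile the visit numbers for the medication record.
- Report treatment changes by arm together with the person-weeks actually covered, so that a difference in capture is visible beside any difference in recorded changes.
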